The study is scheduled to last 24th months. Baseline clinical observation will be done 30 days after placement of adhesion restoration (First data research); a second appointment after 12th months (second data; data not to be included on final report, according to the main purpose and trial hypothesis to study) and the last research evaluation will be at 24th months after baseline (Final data/report). Clinical trial may continue for similar assessment intervals, after 24th months evaluation. This situation requires new analysis according to the clinical and economics conditions, at that time.

2.2- POPULATION AND PARTICIPANT SELECTION

All participants will be informed (Written and verbal Inform Consent, Annex 1) about the trial conditions and purposes, but will not be aware of what tooth will received the adhesion treatment strategy under evaluation. Written informed consent form (Annex 1), according to World Medical Association Declaration of Helsink (31), will be obtained from all participants prior to starting the treatment. University

Ethics Committee review and approved the present protocol. This clinical trial is done according to the European Union law for clinical research and National Law for Clinical Research (Law 21/2014, of 16 April), and was analysed, approved and authorized by the National Competent Authorities

- **CNPD**, Portuguese Data Protection Authority (Authorization and registry 6430/2015 at 7 July 2015; Case 2536/2015).
- **CEIC**, National Ethics Committee for Clinical Research (N.º 20150305; Approved at 3th August 2015)
- INFARMED, National Authority of Medicines and Health Products, IP (N.° EC/011/2015; DPS/DM/450.10.053/2015/0314; Authorization at 4th August 2015)

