In this study will be included participants with clinical diagnosis of tooth structure coronal loss and needs for cervical (vestibular surface) restoration without chemical or bacterial origin, called non-carious cervical lesion (NCCL) located in pre-molars/molars (PM/M) teeth, with cavity dimensions defined in the study design. Therefore, restorations can be made in PM or M teeth; a participant can have up to 16 teeth (8PM + 8M) with NCCL. The number of teeth to restore by participant will be of maximum of 6 and a minimum of one NCCL, within this clinical trial. The allocation of the study arms (G1 to G6) to a particular tooth is randomly allocated, with the information available to the operator/principal investigator in sealed envelopes and previously prepared by the investigator-statistics. The allocation of the study arms (G1, G2, G3, G4, G5, G6) to each tooth by participant is performed randomly, but ensuring that the distribution of the groups is not repeated in the same participant. For this purpose, will be organized by the statistical investigator, 210 envelopes with 35 sequences of 6 study arms, where in each order of 6 groups is randomized.

If the patient has more than six teeth that meet the inclusion criteria, the selection of the PM and M teeth to be included in the clinical trial will be conducted randomly by scenarios randomized by the statistical investigator after participation and contact for the effect (not done a priori, since it is necessary 19448 scenarios prior randomization before observing any patient, whereas the possible teeth to be selected for treatment is between 6 and 16 and the teeth to select from 6).

The participant has as cost the academic/scientific fees, as in usual clinical context of Dentistry School Clinic of **Sector Sector** as "restoration of a tooth surface"/ by tooth to restore (One to six teeth), which of course would have to make even not participating in the investigation, as the Dentistry School Clinic fee scale.

The restorations included in this trial will be evaluated for determine clinical performance from baseline to 24th month by the three calibrated examiners. These observation appointments (three, in two years) as part of the clinical trial will be free of charges for participants. Baseline and 24th month data will be statistically analysing, according to this trial purpose and hypothesis.

2.3-STUDY ADHESION ARMS

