One week, before the Restorative procedure (1st appointment): Inform the patient (Written/Verbal- Anexx-1); Patient signature of informed consent; Fulfilment of the project clinical file (patient identification, general clinical summary, oral clinic examination, oral hygiene state; Annex 2); Dental prophylaxis with fluoride toothpaste and water with a nylon brush. Vitality tests (cold and hot) executed with spray *Endo cool* (ethyl chloride) and warm instrument; Pre-operative sensitivity evaluation by applying air for 10 seconds from a dental syringe placed 2 cm from the tooth surface (16); NCCLs cavities will be evaluated according to the degree (1, 2, 3, 4) of sclerotic dentin (32), cavity dimensions (H-height, W-width, and D-depth) in millimetres (mm) and geometry (evaluated by profile photograph, as Angles Acute (A), Severe (S), Obtuse (O) (16);

1st Appointment-Intervention: Initial intra-oral/cavity surface and tooth digital photography; Teeth anaesthesia with 3% mepivacaine (Scandinibsa, Sintra Business Park, Portugal); Operatory field isolation with cotton rolls and retraction floss (Ultradent)._All cavities cleaned with pumice and water in a rubber cup, followed by rinsing and drying. Selection composite colour by shade guide; Adhesive interventions according to G1 to G6 arms assignment. Adhesive systems will be used as SingleDose mode. Composite restorations (AdmiraFusion Universal nano-hybrid composite) with incremental filling technique (two increments maximum), light-cured (LED Unit) with an intensity of 1000mW/cm2, during 40 seconds. Restorations will be finished immediately with diamond disks (OptiDisc® medium 40μm; Kerr) and burns. Polishing performed with diamond-impregnated silicone polishers (Dimanto, Voco, CuxHaven) during 10 seconds._Intra-oral digital photography of the restoration.

2.6-CLINICAL RECALL

Baseline (30 days after restoration), 12th and 24th months Appointments

1 - Intra-oral digital photography of the NCCL restoration;

2- Pos-operative sensitivity evaluation by applying air for 10 seconds from a dental syringe placed 2 cm from the tooth surface (16);

3 – Clinical direct evaluation by 3 calibrated examiners according to FDI (33) (Annex 3) and USPHS (34) (Annex 4);

4°- Data register.

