Study variable definition_- Clinical/direct observation and performance evaluation acceptance by means of FDI (*FDI World Dental Federation - clinical criteria for the evaluation of direct restorations*) (Adapted from (33) (Annex 3) and USPHS (34) (Annex 4).

2.7- DATA AND STATISTICAL ANALISYS PLAN (SAP)

Data statistical analysis and description according to aims of this trial; Specific program for statistical data analysis (IBM(c) SPSS(c) Statistics vs. 22 or later) will be used. The changes in parameters clinical performance (paired comparison analysis) by both, FDI and USPHS criteria will be assessed by McNemar or Wilcoxon tests, for both

primary and secondary outcomes, to determine differences between treatments with regard to aesthetic, functional and biological parameters from baseline to 24th month recall (longitudinal assessment). Differences will be considered to be significant at P<0.05. Whenever 3 groups will be compared at 24 months' recall, a Kruskal Wallis test will be used and upon significant differences detection, then Mann-Whitney tests considering Bonferroni correction will be used for pairwise group comparisons.

Comparison of FDI and USPHS acceptance (success rate) criteria evaluation outcomes for Esthetic, for Functional and for Biological Parameters, at 24th Month Follow-up, were compared using the chi-square test.

If missing data occurs, that is, if dropouts or non-observed due to loss of retention of the restoration, then the paired comparison will consider for the baseline just the restorations existing at the last moment (24 months).

2.8- OBSERVATIONS REGARDING SAMPLE CALCULATION

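### Lesion factors and pre-operative sensitivity are recorded for each tooth but enter neither the randomisation nor any planned comparison, which costs precision and leaves chance imbalance without a pre-specified response

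*Combined protocol and SAP*

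**What the plan says.** All references are to the combined protocol and SAP.

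- **Recorded before treatment (section 2.5; form in Annex 2).** "NCCLs cavities will be evaluated according to the degree (1, 2, 3, 4) of sclerotic dentin", along with "cavity dimensions (H-height, W-width, and D-depth) in millimetres (mm) and geometry". Sensitivity is tested too: "Pre-operative sensitivity evaluation by applying air for 10 seconds from a dental syringe placed 2 cm from the tooth surface". The Annex 2 grid has yes/no boxes for cold, heat and air, by tooth, pre-operatively and at 1, 12 and 24 months.
- **Randomisation (section 2.2).** 35 random sequences of the six arms, with no arm repeated in a participant. No stratification by a lesion factor is described. Cavity dimensions are named as an eligibility condition.
- **Meaning of baseline (section 2.1).** "Baseline clinical observation will be done 30 days after placement of adhesion restoration". Section 2.2 adds: "Baseline and 24th month data will be statistically analysing, according to this trial purpose and hypothesis".
- **Analysis (section 2.7).** Changes from baseline to 24 months "will be assessed by McNemar or Wilcoxon tests, for both" primary and secondary outcomes. For three groups at 24 months, "a Kruskal Wallis test will be used and upon significant differences detection", Mann-Whitney tests with Bonferroni correction follow. A chi-square test compares FDI with USPHS acceptance. No covariate, stratified analysis, regression model or table of lesion factors by arm is specified.

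**The concern.** The trial measures several characteristics of each lesion that could plausibly affect how a bonded restoration performs, then plans arm comparisons that make no use of them. The protocol itself treats tissue condition as relevant. Its introduction says the choice of adhesive mode depends on it, and the source cited for the sclerosis scale is, by its title, an evaluation of an all-in-one adhesive across degrees of sclerosis.

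Two things are at stake. First, with 35 restorations per arm, arms can differ visibly in lesion mix by chance. If that happens, the SAP offers no agreed response, and choosing covariates after the 24-month data are seen would invite selective adjustment. Second, the introduction mentions the belief that self-etch adhesives cause less post-operative sensitivity. The pre-operative value that would help to attribute later sensitivity is collected but compared with nothing.

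**Working it through.** **The plan's own figures.** 6 arms x 35 = 210 restorations, as in sections 2.2 and 2.8. Section 2.8 says no power analysis was possible. The documents give no prevalence for any lesion factor and no association between a factor and an outcome. There is therefore no planned figure on this point to reproduce, and the sizes below rest on assumed prevalences.

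**Chance imbalance in a yes/no lesion factor.** The 95% range is ±1.96 x sqrt[p(1−p)(1/n1 + 1/n2)], with lesions treated as independent. The group sizes follow from the hypotheses: single arms of 35 (pairwise tests among G1, G4 and G6, for example), 35 v 70 (G1 v G4G6; G2 v G3G5), and 70 v 70 (G1G2, G3G4, G5G6).

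At p = 0.5:
- 35 v 35: 1.96 x sqrt(0.25 x 2/35) = 1.96 x 0.120 = 0.234
- 35 v 70: 1.96 x sqrt(0.25 x (1/35 + 1/70)) = 1.96 x 0.1035 = 0.203
- 70 v 70: 1.96 x sqrt(0.25 x 2/70) = 1.96 x 0.0845 = 0.166

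| Assumed prevalence | 35 v 35 | 35 v 70 | 70 v 70 |
|---|---|---|---|
| 10% | ±14.1 points | ±12.2 | ±9.9 |
| 20% | ±18.7 | ±16.2 | ±13.3 |
| 30% | ±21.5 | ±18.6 | ±15.2 |
| 50% | ±23.4 | ±20.3 | ±16.6 |

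For a continuous factor such as depth, 35 v 35 gives ±1.96 x sqrt(2/35) = ±0.47 SD. In 200,000 simulated allocations, some pair among three arms of 35 differed by at least 20 points with probability 0.13, 0.21 and 0.27 at prevalences of 20%, 30% and 50%.

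**Effect of within-mouth allocation.** If complete six-tooth sequences fall within one participant and lesions in a mouth resemble each other, the range becomes ±1.96 x sqrt[2p(1−p)(1−ICC)/35]. At p = 0.5 this is ±19.6 points for an assumed ICC of 0.3 and ±16.6 for 0.5. Participants may contribute only one to six teeth, so this protection may be partial.

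**What an imbalance does to an arm difference.** The shift is the imbalance multiplied by the risk difference due to the factor. With assumed risks, a 20-point imbalance gives 0.20 x (0.25 − 0.05) = 4 points, or 0.20 x (0.40 − 0.10) = 6 points.

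**Sensitivity.** Four possible air-test histories for a tooth:

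| Pre-operative | 30 days | 24 months | Pair seen by the planned test |
|---|---|---|---|
| Yes | Yes | Yes | Yes–Yes |
| No | Yes | Yes | Yes–Yes |
| Yes | No | No | No–No |
| No | No | No | No–No |

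McNemar's test uses only pairs that change, so all four contribute nothing. Rows 1 and 2 look the same, as do rows 3 and 4. Anything that happened between the pre-operative test and day 30 is absorbed into the baseline. The between-arm test of 24-month scores does not separate row 1 from row 2 either.

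**The case against.** The strongest reply is that nothing in the stated comparisons is wrong. Allocation is random, so chance imbalance is already part of the sampling error that the P-value reflects. The scored outcomes are explicitly post-operative sensitivity, and a randomised comparison at 24 months is fair without the pre-operative value. Section 2.7 also promises description of the data, and nothing forbids a table of lesion factors by arm. All of this stands, and it limits the point to precision, attribution and pre-specification.

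Four stronger readings are tempting but unsupported:

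- **That the unadjusted tests are biased or invalid.** Failure to adjust for lesion factors does not make them so, because the arms are randomised.
- **That the planned tests could not use any of these measurements.** McNemar's test could take the yes/no pre-operative air response directly. The obstacle is that baseline is defined as day 30. What the named tests, as planned, do not provide is covariate adjustment of an arm comparison.
- **That the lesion factors have no role at all.** Cavity dimensions are an eligibility condition.
- **That adjustment would be worth a stated number of extra restorations.** The documents report no result showing that sclerosis, depth or geometry predicts outcome. The usual 1/(1−R²) conversion belongs to a linear model of a continuous outcome and does not carry over to a proportional-odds model.

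It is also fair to object that adjustment may be fragile. The three USPHS biological items (sensitivity, caries, gingival bleeding) have only two levels in Annex 4 and may be as sparse as retention. No event rate is given for any item.

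**Conclusion.** The point holds as a matter of efficiency and pre-specification; it does not call the validity of the tests into question. Lesion factors and pre-operative sensitivity are collected and then left out of randomisation and of every planned comparison. The plan therefore gives up whatever precision they would bring and has no agreed response to a visible imbalance.

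The 23-point figure is the least favourable case: two single arms of 35, 50% prevalence, independent lesions. The pooled hypotheses face about 20 or 17 points under the same assumptions, and lower prevalence or within-mouth similarity reduces these further. The gain in precision cannot be quantified from the documents.

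The sensitivity part needs no assumed figures. It follows from baseline being set 30 days after treatment and from the analysis being limited to that visit and 24 months. The change should be made, because it draws on data already planned for collection.

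**What to change.** Amend section 2.7 to:

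1. Tabulate sclerosis grade, cavity dimensions, geometry and pre-operative air response by arm.
2. Pre-specify an adjusted between-arm analysis at 24 months, reported beside the unadjusted one. Use an ordinal or binary model that accounts for participant, with a small fixed set of recorded covariates, for example sclerosis grade and cavity depth.
3. Add the pre-operative air response as a covariate for the FDI and USPHS sensitivity items. Where such an item is two-level or sparse, make this the single covariate.
4. For any other sparse or two-level item, such as retention or secondary caries, allow at most one covariate and use a penalised or stratified exact method.
5. Fix the covariates before the 24-month data are seen.

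The cost is SAP wording and modest analysis work, with no new visits or measurements. There are two drawbacks. Models may be unstable when events are few, which is why the covariate set is capped. The adjusted odds ratio is also conditional on the covariates and will not be numerically the same quantity as the unadjusted one, so both should be labelled clearly.

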H0 – Bonding to NCCLs with FBDC-SE (G1) and MM-SE(G4G6) result in similar restorations (aesthetic, functional and biologic) success rates;

H0 – Bonding to NCCLs with FBDC-SE (G1) and MM-SE (G4G6) adhesives result in similar restoration retention rates;

H0 – Bonding to NCCLs with FBDC by SE and enamel etching mode (FBDC-SE-EE; G2) and MM adhesives by Etch-and-Rinse mode (MM-ER; G3G5) result in similar (no significant differences) clinical (aesthetic, functional and biologic) behaviour/performance;

H0 – Bonding to NCCLs with FBDC-SE-EE (G2) and MM-ER (G3G5) result in similar restorations (aesthetic, functional and biologic) success rates;

H0 – Bonding to NCCLs with FBDC-SE-EE (G2) and MM-ER (G3G5) result in similar restoration retention rates;

H0 – Bonding to NCCLs with FBDC (G1G2) or FBU (G3G4), DC adhesives, and ADU (G5G6) light-curing adhesive, with SE or SE-ER/ER modes result in similar (no significant differences) clinical (aesthetic, functional and biologic) behaviour/performance;

H0 – Bonding to NCCLs with FBDC (G1G2) or FBU (G3G4) and ADU (G5G6) lightcuring adhesive, with SE or SE-ER/ER modes result in similar restorations (aesthetic, functional and biologic) success rates;

H0 – Bonding to NCCLs with FBDC (G1G2) or FBU (G3G4) and ADU (G5G6) lightcuring adhesive, with SE or SE-ER/ER modes result in similar restoration retention rates;

H0 - FDI or USPHS criteria evaluation outcomes not differ for the same data, at 24th month follow-up.

2 – POPULATION, MATERIALS AND METHODS

2.1- TRIAL DESIGN

The trial design follows the Consolidated Standards of Reporting Trials (CONSORT) statement (30). Prospective, double blind, clinical trial; randomized allocation of NCCL restorations by six adhesion interventional groups (6 arms) for examination of restorations performance.

Study will take place in University

Dentistry School Clinic. Participants recruitment between November 2015 and April 2016. Restorations estimated to be done until April or May 2016 year.

-

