For the operator calibration procedure, operator will do one restoration of each group in order to identify all steps involved in the application technique. This procedure will be done three times, with one week, interval. All restorations done by the same calibrated operator. Three experienced and calibrated dentists, not involved with the restoring procedures and therefore blinded to the group assignment, will perform the clinical evaluation. For training purposes, the examiners observed 10 photographs that were representative of each score for each criterion, in 10 cervical restorations (not included in this trial), each one, on two consecutive days. An intra-examiner and inter-examiner agreement will be calculated.

Medical devices composition according to manufactures, Voco and Ivoclar Vivadent safety data sheets for adhesives and products is show in Table 2.

safety data sheet).	
Medical Device	Composition
(manufacture)	
Lot#Number	
Futurabond [®] DC (FBDC)	Liquid 1. Acidic adhesive monomer*; BIS-GMA (5-10%), 2-HEMA (5-10%);
(Voco, Cuxhaven, Germany)	Liquid 2. Ethanol (50-100%); Initiator (2.5-5%)
Lot# 1532592	Mixture. organic acids, BIS-GMA, 2-HEMA, TMPTMA, campherchinon,
	amines (DABE), BHT, catalysts, fluorides and ethanol
	pH-value 1.5
Futurabond [®] U (FBU)	Liquid 1. (2-HEMA) (25-50%); BIS-GMA (25-50%); HEDMA (10-25%);
(Voco, Cuxhaven, Germany)	Acidic adhesive monomer (5-10%)*; UDMA (5-10%); catalysts ($\leq 2.5\%$),
Lot# 1543141	silica nanoparticles;
	Liquid 2. Ethanol (50-100%); Initiator (2.5-5%); catalysts (≤ 2.5)
	pH-value 2.3
Vococid®	35% orthophosphoric acid
(Voco, Cuxhaven, Germany)	
Lot# 152135	
Adhese® Universal (ADU)	Liquid: 2-HEMA (10-<25%); Bis-GMA (10-<25%); ethanol (10-<25%); 1,10-
(Ivoclar Vivadent AG,	decandiol dimethacrylate (3-<10%); Methacrylated phosphoric acid ester (3-
Liechtenstein)	<10%); campherquinone (1-<2.5%); 2-dimethylaminoethyl methacrylate (1-
Lot# U35131	<2.5%); 2-dimethylaminoethyl methacrylate (0.1-<2.5%).
	pH-value 2.5-3.0
Admira [®] Fusion	Nano-hybrid ORMOCER®s (organically modified ceramics); large and
(Voco, Cuxhaven, Germany)	precondensed molecules of an inorganic matrix with a high degree of cross-
Lot# (Shade A1, A2, A3, A3,5)	linking. 84 % w/w inorganic fillers. Silicon oxide forms the chemical base, not
1508270, 150827, 1510508,	only for the fillers (nanofillers as well as glass ceramics) but also for the resin
1509381	matrix.

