Vitaliy	taliy Tooth Pre		Pre-operative		1 st Month		12 th Months		24 th Months	
Test	Number	Yes	No	Yes	No	Yes	No	Yes	No	
Cold										
Heat										
AIR										
Cold										
Heat										
AIR										
Cold										
Heat										
AIR										
Cold										
Heat										
AIR										
Cold										
Heat										
AIR										
Cold										
Heat										
AIR										

4- DENTIN SCLEROSIS/ 5 - CAVITY DIMENTIONS (HWD) /6 – GEOMETRY ______ / H-_____W-____D-___ /____

 Date
 NCCL N°
 Randomized allocated Group treatments
 Material

 1 1

 2

 3

 4

 5

 6

Code of patient_____

	FDI Ci	riteria				_	/ /	
NGCI	A) ESTHETIC PROPERTIES		B) FUNCTIONAL PROPERTIES		C) BIOLOGICAL PROPERTIES			
NCCL	1.	2.	3.	4.	5.	6.	7.	8.
Number	Surface	Surface	Colour	Fractures and	Marginal	Postoperative	Recurrence	Tooth
	Luster	Staining	stability and translucency	retention	Adaptation	Hipersesibility, tooth vitality	of Caries	integrity (enamel cracks)

	USPHS Criteria - / /							
NCCL	A) ESTHETIC PROPERTIES			B) FUNCTIONAL PROPERTIES		C) BIOLOGICAL PROPERTIES		
Number	Surface	Marginal	Color	Retention	Marginal	Postoperative	Secondary	Gingival
Truiniber	Staining	Discoloration	Match		Integrity	Sensitivity	Caries	Bleeding
					(Adaptation)			

Code of patient_____

Category	Criteria
Category	Crittina
1	No sclerosis present; dentin is light yellowish or whitish, with little discoloration; dentin is opaque, with little translucency or transparency
2	More sclerosis than in category 1 but less than halfway between categories 1 and 4
3	Less sclerosis than in category 4 but more than halfway between categories 1 and 4
4	Significant sclerosis present; dentin is dark yellow or even discolored (brownish); glassy appearance, with significant translucency or transparency evident

DENTIN SCLEROSIS CLINICAL SCALE (adapted from (32)

CAVITY DIMENTIONS (adapted from (16))

CAVITY	Height	Width	Depth	
DIMENSIONS				
(HWD)(mm)				
Cavity dimensions in millimetres (mm)				

CAVITY GEOMETRY CRITERIA (adapted from (16))

Category	Criteria evaluated by profile photograph
Acute (A)	< 45°
Severe (S)	45°- 90°
Obtuse (O)	> 90°

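### Both scales are graded in one step by the same panel, with scoring order and masking unspecified, so carry-over can inflate FDI–USPHS agreement

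*Combined protocol and SAP*

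**What the plan says.** - Section 2.6, step 3, is a single grading step: "Clinical direct evaluation by 3 calibrated examiners according to FDI (33) (Annex 3) and USPHS (34) (Annex 4". The same list of steps serves all three recalls: "Baseline (30 days after restoration), 12th and 24th months Appointments".
- Section 2.2 says that the trial restorations "will be evaluated for determine clinical performance from baseline to 24th month by the three calibrated examiners".
- Section 2.4 describes the examiners as "not involved with the restoring procedures and therefore blinded to the group assignment, will perform the clinical evaluation". That blinding covers the adhesive group, not the other scale's grade. On agreement, the section says only: "An intra-examiner and inter-examiner agreement will be calculated".
- The research file in Annex 2 prints an FDI grid and then a grid titled "USPHS Criteria", both indexed by lesion number.
- The last null under Objectives and Hypothesis is that "FDI or USPHS criteria evaluation outcomes not differ for the same data, at 24th month follow-up". Section 2.7 tests it on acceptance for the esthetic, functional and biological parameters, which "at 24th Month Follow-up, were compared using the chi-square test".

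No section states which scale is scored first, whether that varies, whether the order is recorded, or whether the first grades are out of sight while the second scale is scored. No section divides the scales between examiners.

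**The concern.** Comparing the two scales is a declared hypothesis with its own test. The comparison is informative only to the extent that the second grade is a fresh judgement. Retention, marginal adaptation, colour, surface staining, sensitivity and caries appear on both Annex 2 grids. An examiner who has just graded a margin on one scale is likely to be guided by that grade on the other. Carry-over of this kind pulls the grades together, so a finding of no difference between the scales is the result that the procedure itself favours.

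A real difference is plausible. The Introduction cites an 18-month study of a universal adhesive in which the two use modes differed in marginal adaptation by FDI but not by USPHS.

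A second, weaker issue is order. If the scale scored second were graded systematically more or less strictly, that shift would enter the FDI–USPHS difference. With order neither varied nor recorded, it could not be estimated or removed afterwards.

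**Working it through.** **Inputs from the documents.** Section 2.8 gives 35 restorations in each of six arms: 6 × 35 = 210, which reproduces the stated total. Section 2.7 sets significance at P<0.05. The documents give no acceptance rates, no discordance between scales, and no size for carry-over or order effects.

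**Assumptions.** 200 of the 210 restorations are graded at 24 months, each with one acceptable/unacceptable result per scale. Restorations are treated as independent, although a participant may contribute up to six. Tests are two-sided at 0.05.

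**1. Carry-over.** Suppose 8% of restorations are unacceptable on one scale only and 2% on the other scale only. If a share c of discordant grades is pulled into agreement, both rates are multiplied by (1 − c). The approximate paired statistic is (b − d)/√(b + d), where b and d are the two discordant counts. For the chi-square, a further 5% are assumed unacceptable on both scales. Its statistic is approximately the difference divided by √(2p(1 − p)/200), with p the pooled unacceptable rate.

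| c | b, d | Paired statistic | Exact McNemar power (simulated) | Unacceptable rates | Chi-square statistic (root) | Chi-square power on paired data (simulated) |
|---|---|---|---|---|---|---|
| 0 | 16, 4 | 12/√20 = 2.68 | about 73% | 13% v 7% | 0.060/0.0300 = 2.00 | about 51% |
| 30% | 11.2, 2.8 | 8.4/√14 = 2.24 | about 54% | 10.6% v 6.4% | 0.042/0.0279 = 1.51 | about 23% |
| 50% | 8, 2 | 6/√10 = 1.90 | about 36% | 9% v 6% | 0.030/0.0263 = 1.14 | about 8% |

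The apparent difference shrinks from 6 points to 4.2 and 3. The McNemar figures do not depend on the 5% joint rate. The chi-square figures do: the more restorations fail on both scales, the lower its power.

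**2. A second model.** With 210 restorations, true acceptance of 95% (FDI) and 88% (USPHS), 2% random mis-scoring, and the second grade copied from the first with probability 0, 0.25, 0.5 or 0.75, the observed difference is about 6.7, 5.0, 3.4 and 1.7 points. Exact McNemar power is about 0.85, 0.71, 0.48 and 0.15. Alternating the order gives nearly the same figures at each level, so alternation alone does not remove carry-over. With equal true acceptance (95% on both), copying lowers the McNemar rejection rate from about 2% towards zero. It creates no false difference.

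**3. Order effect, if one existed.** Take equivalent scales with 2% random discordance each way and 8% unacceptable on the first-scored scale, then add 3 or 5 points to the second.

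| Order effect | Expected discordant counts of 200 | McNemar false rejection | Chi-square on paired data |
|---|---|---|---|
| 3 points (8% v 11%) | 10, 4 | about 27% | about 7% |
| 5 points (8% v 13%) | 14, 4 | about 59% | about 31% |

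If half the participants start with each scale, the mean difference returns to about 0 and McNemar rejection to about 3%.

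**4. First-scored grades only.** This comparison is free of carry-over but uses about 100 restorations per scale from different participants. With the rates in step 1, 13% v 7%, the standard error is √(0.13 × 0.87/100 + 0.07 × 0.93/100) = 0.042. The ratio is 0.06/0.042 = 1.42, so power is about Φ(1.42 − 1.96), or 30%. If no restoration failed on both scales (8% v 2%), it would be about 50%.

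**The case against.** Several points on the other side stand.

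- **No fixed order.** A reader might infer from the Annex 2 layout that FDI is always scored first. The documents do not say so. They print one grid before the other and are silent on sequence. Nor do they say outright that each examiner scores both scales on every restoration, although that is the natural reading.
- **No repeated stimulus.** A reader might suppose that sensitivity provoked while scoring the first scale is then recorded on the second. Section 2.6 places the air test in step 2, before grading, and the Annex 2 form has one entry per stimulus, tooth and visit. Nothing describes a second stimulus. Gingival bleeding is scored only on USPHS, so a difference arising there is mainly one of scale content.
- **A difference remains interpretable.** It would go too far to say that the comparison cannot separate the scales from scoring order. Copying biases only towards agreement, so an observed difference would still carry information, though a directional order effect could not be excluded.
- **Chi-square error rates.** Treating the two sets of grades as independent samples would give false rejection of 17% and 37% for the 3- and 5-point effects. The grades are paired, and the corresponding figures are about 7% and 31%.
- **Limited reach.** This is the last of ten nulls. The trial's main purpose is to compare adhesives, and examiners are blinded to group.

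Scoring the same restoration on both scales is itself the intended design. That supports a paired comparison but does not make the second grade independent of the first. Silence on order does not help either, because an unrecorded order cannot be adjusted for.

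**Conclusion.** The point holds as an avoidable weakness in one declared hypothesis. One panel grades both scales in one step, six features overlap, and neither order nor masking is addressed. Retaining the tenth null would therefore be weak evidence that the scales agree.

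Under the assumed rates, the loss of power is moderate to large: from about 73% to between 54% and 36% with McNemar, and from about 51% to between 23% and 8% with the planned chi-square. The order-effect figures are conditional on an effect for which the documents offer no evidence. All sizes rest on assumed discordance, joint failure and carry-over rates, and on independence between restorations. The direction of the carry-over bias does not depend on those values. Comparisons between adhesive arms within either scale are not affected. The change is worth making because it is cheap; confidence is medium because the size of the effect is unknown.

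**What to change.** **Section 2.6, step 3.** Alternate the starting scale by participant, for example by odd or even participant code, and record the order. Score all of a participant's lesions on the starting scale, and hand in that sheet before the second scale begins.

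**Annex 2.** Put the two grids on separate sheets.

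**Section 2.7.** Estimate the paired FDI–USPHS difference within each order and average the two estimates. Report the comparison of first-scored grades as a low-power sensitivity check.

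Alternation cancels a constant order effect. Separate sheets reduce carry-over but do not eliminate it, because the examiner may remember the tooth; the report should say so.

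**Cost.** A short addition to 2.6, two sheets in place of one form, and a short addition to the SAP. No extra visits, staff or procedures. The downside is slightly more form handling and chair time.
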